## **8.0 PROTECTION OF HUMAN PARTICIPANTS**

The protocol for this study will meet approval by the University of Michigan Institutional Review Board prior to initiating any of the described study activities.

### **D 1. Human Participants Involvement And Characteristics Removing Participants From The Protocol.**

Respondents who meet eligibility criteria will be invited to participate in the baseline screening assessment. While we have chosen the above eligibility criteria based on

previous work, we will make adjustments to the future, larger trial, based on the results and feedback from our proposed pilot.

## D 2. Sources Of Materials

For Phase II (intervention), data will be collected through the following methods: finger stick capillary blood samples, blood pressure measurements, weight, and height. Data that are obtained specifically for research purposes will be collected only with informed consent. All data will be collected over the course of the award period.

## D 3. Potential Risks

Participation in this study involves minimal foreseeable risks. Participants will be asked to provide finger stick capillary blood samples during assessments. Risks associated with finger stick capillary blood draws include: minor discomfort from obtaining the blood sample, minor pain, bruising, or bleeding at the puncture site similar to any other routine blood sample collections. With self-report surveys, there is also the small risk that prompting patients to review their diabetes care practices and providing them with feedback about their diabetes-related health outcomes (e.g., A1C, blood pressure) could cause some emotional discomfort or anxiety. Such discomfort would likely prime patients and their primary care physician or group facilitator to address any problems identified. Other risks include breach of confidentiality of study data.

### Protection Against Risk

All questionnaires and instrumentations are standardized measures that have been used in our own trials and in other diabetes research and there are no significant risks anticipated related to the completion of them. However, breaks will be given as needed to reduce fatigue, or measures read to adolescents, and research assistants will be appropriately trained to obtain personal information in a sensitive fashion. Research staff will be trained in research ethics, confidentiality protection, and HIPAA prior to and throughout the study period.

At the time of study enrollment, participants will be assigned a study identification number to be used in all study materials and data for the duration of the study. All identifying information will be separated from the data and laboratory values. A master list that contains participants names and study identification number will be kept in a locked filing cabinet in the School of Social Work. The principal investigator ([name]) and the research assistant will be the only persons who have access to the file linking study ID# to each subject. Participants will be assured that all data they provide to the study will be confidential, unless it is necessary to "alert" both the patient

and their physician because of a laboratory value outside of the normal ranges that reflects a risk requiring immediate attention. All reports will use aggregate data. Subject names or other identifiers will not be reported. No persons from the DCHC or other community based location will handle or have access to personal health information or participant survey data.

#### **D 6. Potential Benefits Of The Proposed Research To The Participant And Others**

Participants will have the potential to benefit from the study by receiving free diabetes self-management education and support from the intervention and also an opportunity to discuss barriers and facilitators to recruitment and retention of men and women in a large-scale intervention. There are also benefits to society from the research through its potential to improve diabetes self-management interventions for persons with Type 2 diabetes. We feel the benefits of participating in this study significantly outweigh the risks.

### **9. DATA AND SAFETY MONITORING PLAN**

**Adverse Events:** The PI will monitor adverse events throughout the clinical trial period. To ensure staff participation in data safety and monitoring activities, all members of the project team (research assistants and staff) will be trained on the specifics of the data safety and monitoring plan. Field staff will be trained on what constitutes an adverse event to a participant and instructed to report any adverse events immediately to the principal investigator, [name].

For the purposes of this study, adverse events will be considered any undesirable sign, symptom, or medical condition occurring during the study, whether or not related to the intervention. Adverse events include new events not present during the training period or events that were present during the training period but increased in severity over time. Each adverse event will be recorded and assessed for its date of onset, duration, severity, seriousness, and relationship to study treatment, and any action/treatment that is required. All adverse events will be collected, analyzed, and monitored using an adverse event form. Furthermore, the committee will establish “alert” values for A1C and blood pressure. The PI will notify the subject and the subject’s physician whenever there are laboratory results above these values because of the clinical implications of a value substantially out of normal range.

All serious medical events will be reported within one business day of their identification. All serious, fatal or life-threatening adverse events will be reported to UM IRB and the NIH within 24 hours of its identification. All causes of death are considered to be serious medical events. Unexpected moderate or severe adverse events will be reported in writing to the IRB and NIH. Serious medical events will be collected throughout the

intervention phase of the study. The PI, along with the study psychologist [name] [name] will adjudicate whether or not each serious adverse event may be attributable to study participation. Events that involve an unexpected adverse event and are possibly or probably related to participation in the study will be reported to the IRB at University of Michigan within one business day. Annual reporting of aggregate adverse events to the IRB and NIH will be performed. All research project personnel will complete training in the protection of human research participants. The PI and research assistant will verify appropriate reporting of adverse events, quality of data collection, and adherence to the study protocol. Participant dropout rate will also be monitored and reviewed for needs or trends based on specific participant characteristics.

**Data Safety & Monitoring Board:** The DSMB will hold a minimum of two conference calls over the award period (approximately two hours per call) to discuss the progress of the intervention and review research results, if applicable. At the first meeting, the board will elect a chair of the DSMB. To facilitate these conference calls, the principal investigator will prepare a report on the progress of the project to date. This report will be circulated well in advance of the conference call to allow all members ample time to read it. These calls will be scheduled and organized by the study coordinator and will be held at a time convenient for all members.

The DSMB is responsible for assuring that study participants are not exposed to unnecessary or unreasonable risks and that the study is being conducted according to high scientific and ethical standards. Specifically, the DSMB will:

1. Assess the performance of the study with respect to subject recruitment, retention and follow-up, protocol adherence, and data quality and completeness, in order to ensure the likelihood of successful and timely milestone completion.
2. Monitor interim data regarding the safety of the study, including adverse events. The DSMB may, at its discretion, examine effectiveness data as well.
3. Review abstract and publications of main findings prior to submission to ensure the study is being reported appropriately.
4. Review and consider any protocol modifications or ancillary studies proposed by the study investigators after the main study begins to ensure that these do not negatively impact on the main trial.
5. Advise the NIA and the study investigators as to whether a protocol should continue as scheduled or undergo a modification due to a finding from the monitoring process.

6. Make recommendations to the NIA and principal investigator concerning continuation or conclusion of the trial.

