## **Online Diabetes Education Project: Virtual Diabetes Self-Management Education and Support Intervention IRB Protocol**

### **1.0 PHASE II RESEARCH PLAN (Pilot Randomized Control Trial, 3 months)**

During Phase II we will be conducting a 3 month pilot randomized controlled trial (RCT) of Virtual Diabetes-Self Management Education and Support (DSME/S), the treatment adapted in Phase I, to evaluate participant recruitment and retention rates, treatment and intervention satisfaction and estimate intervention effect sizes on our primary outcome of glycemic control (HbA1c) as well as on secondary outcomes such as diabetes-related distress, self-management behaviors and diabetes social support at baseline and treatment termination. Data will be collected at baseline and three months (treatment termination) at a federally qualified health center, telephonically, or virtually. Participants will be randomized to the virtual empowerment-based DSMES or a control group. All virtual DSME intervention group sessions will be held on an online platform, Zoom Med. The baseline assessment and intervention period will consist of 14 weeks. In the first 2 weeks participants will complete baseline questionnaires, interviews, and physiologic testing at a federally qualified health center, telephonically, or virtually. In weeks 3 to 10, participants will be simultaneously enrolled in 8 weekly virtual DSME classes. In weeks 13 and 14 of the intervention, participants will complete the post-treatment assessment battery (See Table 1). Patients who do not complete the intervention phase will also be invited to participate in the treatment termination assessment. The physiologic testing part of the assessment will be held at Detroit Community Health Connection, Inc. (DCHC) and other community-based locations TBD, based on participant feedback, telephonically, or virtually. DCHC is a non-profit community-based primary care organization that provides medical and dental services to the insured, uninsured and underinsured at six federally qualified health centers in the city of Detroit. Data analyses and dissemination of study findings are anticipated to be completed in months 11-12 of the study funding period. In Phase III of this project, we will be conducting qualitative interviews to better understand the acceptability and sustainability of the intervention as routine practice in a community-based clinic.

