**Randomization** Participants will be randomized to the virtual empowerment based DSME/S or a control group using a 50/50 randomization scheme. Participants will be aware if they are in the intervention group or the control group.

**Intervention (virtual empowerment-based DSME/S n=30)** Participants randomized into the virtual empowerment-based DSME/S group will receive 10 hours of DSME/S delivered by a Certified Diabetes Care and Education Specialist (CDCES) over 8 weeks delivered via the Zoom for Health at U-M service may be used for Protected Health Information (PHI, regulated by HIPAA). To ensure treatment fidelity, three DSME/S sessions will be selected at random and recorded and rated for fidelity to the above content by our research team.

**Control Group (Control n=30)** Participants randomized to enhanced usual care will receive referrals to community mental health providers, pedometers, gym memberships to a community-based venue, and intervention patient manuals. Based on several years of experience in Detroit, providing all participants with referrals, pedometers, and educational materials minimizes ethical concerns regarding assignment of underserved populations to receive a no-treatment control.

**Follow-Ups** Follow up assessments for both the virtual empowerment-based DSME/S group and control group will occur at three months (post-treatment assessment). Participants will return to the DCHC for follow-up assessments, telephonically, or virtually and the same measurements and surveys will be completed. Participants will be compensated \$20 for completing each assessment. Data will be stored in REDCap, a secure, web-based application hosted at UM.

**Maintenance of Samples** Strategies will be used to encourage attendance of group sessions and to complete follow up interviews. Reminder emails, texts and/or calls

will be sent before each session to remind participants by the study team. In addition, the study team will collect participant contact information from baseline through the follow up phase. The study team will also ask participants to provide additional contact person(s) that the study team can contact if they cannot reach the participant.

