### **Secondary Outcome Measures**

BMI will be calculated using height and weight. Height will be measured using a stadiometer. Weight will be measured on a high quality, calibrated digital scale. BP will be measured using the auscultatory method.

Diabetes Social Support will be measured using the Diabetes Social Support Questionnaire. Diabetes-related Distress will be measured using Diabetes Distress Scale (SF-12) and lastly, a validated Diabetes Quality of Life will be used to measure quality of life. Participants will also complete questionnaires that assess socio-demographic, behavioral, psychosocial, and health services utilization and are

validated in diverse populations with diabetes.

**Specific Aim 1:** Qualitative analyses will be conducted during the development phase and on the post-intervention focus groups and interviews. First, we will develop codes utilizing a grounded theory approach and will start with the formulation of categories and definitions developed directly from the text. Content from transcripts will be coded for themes and patterns. Through this process a coding manual and definitions will be finalized. The refined manual will be used to guide ongoing coding and pairs of coders will read subsequent transcripts keeping codes that achieve 80% agreement on code application. Analyses will be conducted using Dedoose. This data will be used to conduct a final refinement of treatment content as needed.

**Specific Aim 2:** The proposed study includes a sample size of 60 Black men and women, 30 in the intervention arm and 30 in the control arm. We will assess the impact of the intervention on HbA1c (primary outcome) and diabetes management (secondary outcomes) using multilevel modeling, with intervention group as a between-subjects factor (2 levels) and time as a within subjects factor (3 levels). HbA1c, depression symptoms, diabetes self-management, and social support at baseline and 3 months will be used as the dependent variables. Independent variables include intervention group, time of assessment, and interaction between time and intervention group. Random effects will be allowed for the intercept (to allow differences in baseline measurements) and the slope (to allow differences in the trajectories of change). Covariates e.g. length of time since diabetes diagnosis, age will be tested as predictors of the outcome and retained if significant at  $p < .10$ .

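### No adverse-event question is common to both arms, and scheduled contact between assessments is eight classes against none, so event counts risk unequal ascertainment and control-arm events may surface weeks late or never

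*Combined protocol and SAP*

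**What the plan says.** Section 9 defines an adverse event as "any undesirable sign, symptom, or medical condition occurring during the study, whether or not related to the intervention", so control-arm events count in full. Field staff are "instructed to report any adverse events immediately to the principal investigator", and section 6.0 repeats this. Section 9 then states: "All adverse events will be collected, analyzed, and monitored using an adverse event form". It says serious medical events are collected during the intervention phase, which gives a period but not a method. The reporting deadlines run from the time an event is identified.

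The two arms have different contact calendars. Section 1.0: "In weeks 3 to 10, participants will be simultaneously enrolled in 8 weekly virtual DSME classes". Section 5.0 adds that reminder emails, texts or calls "will be sent before each session to remind participants by the study team". Under the same section, controls "will receive referrals to community mental health providers, pedometers, gym memberships to a community-based venue, and intervention patient manuals", with no study contact scheduled until the post-treatment assessment in weeks 13 and 14, which both arms attend.

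The follow-up assessment repeats the baseline measurements and surveys. Section 7.0 includes one relevant instrument: "Participants will also complete questionnaires that assess socio-demographic, behavioral, psychosocial, and health services utilization". Nothing links its answers to the AE form. Section 4.0, under Recruitment, says the university study team has no access to patients' electronic medical records.

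**The concern.** An all-cause AE definition needs a way of finding events that works equally in both arms. Here the described route depends on staff learning of an event, and the occasions for learning of one differ by arm. No AE question appears in the procedures (section 5.0), in the lists of data to be collected (sections 5.0 and D 2) or in the measures (section 7.0).

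Two things are at stake. First, section 9 asks the Data Safety and Monitoring Board to monitor interim safety data and to advise on continuing or modifying the protocol. Before participants reach week 13, it could see events from an arm with up to 8 scheduled contacts beside an arm with none. A higher count in the DSME/S arm could not be separated from closer observation, and a low count in the control arm would not reassure. Second, a serious event in a control could come to light weeks after onset and still meet every reporting deadline. The pilot is also meant to shape the protocol of a larger trial, which could inherit the same arrangement.

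**Working it through.** The plan gives no AE rate, capture rate or detection lag, so there is no stated figure to reproduce. The lag can be derived from the contact calendar.

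**Inputs from the plan:** 30 participants per arm (section 5.0); classes in weeks 3-10 and post-treatment assessment (T1) in weeks 13-14 (section 1.0); 20% attrition (Power Analysis, section 7.0).

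**Assumptions:** events fall uniformly in time; each is found at the next scheduled contact; all classes are attended; classes fall mid-week, at elapsed weeks 2.5, 3.5, ..., 9.5; T1 falls mid-week 13 (12.5) or mid-week 14 (13.5). Session reminders are not counted.

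**1. Scheduled contacts between baseline and T1:** 8 in DSME/S, 0 in control.

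**2. Lag for events in weeks 3-10 (elapsed 2 to 10, midpoint 6).**

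- Control mean = T1 − midpoint: 12.5 − 6 = 6.5 weeks, or 13.5 − 6 = 7.5 weeks. Range: 12.5 − 10 = 2.5 to 13.5 − 2 = 11.5 weeks.
- DSME/S: half a week before the first class (mean lag 0.25), seven weeks between classes (mean 0.5), and half a week after the last class (mean 2.75 or 3.75).
  - T1 in week 13: (0.5×0.25 + 7×0.5 + 0.5×2.75)/8 = 5.0/8 = 0.625 weeks.
  - T1 in week 14: (0.125 + 3.5 + 0.5×3.75)/8 = 5.5/8 = 0.69 weeks.
  - The maximum is 3 to 4 weeks, for an event just after the last class.

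**3. Lag for events in weeks 3-12 (midpoint 7).** In weeks 11-12 neither arm has a scheduled contact.

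- Control mean: 12.5 − 7 = 5.5, or 13.5 − 7 = 6.5 weeks.
- DSME/S mean: (0.125 + 3.5 + 2.5×1.75)/10 = 0.80, or (0.125 + 3.5 + 2.5×2.75)/10 = 1.05 weeks.

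**4. Participants with no later contact.** If the planned attrition applies equally to both arms, 0.20 × 30 = 6 controls would have no scheduled contact after baseline.

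**5. Effect on counts.** Recorded events = 30 × true risk × share captured. With an assumed true risk of 20% in both arms (6 events each):

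| Captured, DSME/S v control (assumed) | Recorded events | Ratio |
|---|---|---|
| 90% v 90% | 5.4 v 5.4 | 1.00 |
| 90% v 70% | 5.4 v 4.2 | 1.29 |
| 90% v 50% | 5.4 v 3.0 | 1.80 |
| 70% v 30% | 4.2 v 1.8 | 2.33 |

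The ratio depends only on the two capture shares, not on the true risk. The first row applies if T1 recovers control events as fully as the classes do.

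**The case against.** The strongest reply is that no planned analysis is damaged. The model in section 7.0 covers HbA1c, depression symptoms, self-management and social support. The pilot's aims are recruitment, retention, satisfaction and effect sizes. Section 9 plans aggregate AE reporting and board review, with no test between arms. Section D 3 describes minimal risk, chiefly finger-stick effects, discomfort from surveys and loss of confidentiality. The first two arise at assessments, where staff meet both arms alike. With 30 per arm, even 5 events against 3 gives a Fisher p of 0.71. All of this stands, and it limits the importance of the point. It does not supply a way of finding all-cause events in controls.

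A reader might infer more than the documents support:

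- That staff contact is the *only* route and is *absent* for controls. The plan has a central office number, appointment reminders, and collection of contact details through follow-up, none restricted to one arm. What can be said is that only one route is described and that no control contact is scheduled. None of these contacts is described as asking about AEs.
- That the data *are* biased and would make the intervention look less safe. No section says AEs are asked about in class either, so capture may be incomplete in both arms, and equal capture is possible.
- That controls alone carry activity-related exposure. The control paragraph lists pedometers but then says they go to all participants. Only gym memberships are listed for controls alone.
- That deadlines running from identification are a fault. An event cannot be reported before it is known. The weakness is in how events come to be identified.

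The absence of an AE question is a statement about the text available. Material between sections 6.0 and 7.0 was not available to this review.

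**Conclusion.** The point holds as a risk of differential ascertainment, not as demonstrated bias. The plan commits to collecting all AEs of any cause, yet describes only staff reporting, schedules 8 contacts against 0 between assessments, has no access to medical records, and names no AE question at 3 months. The difference in scheduled contacts is read directly from the plan. The lag (a mean of 6.5-7.5 weeks in control against 0.6-0.7 weeks in DSME/S for events in weeks 3-10) rests on uniform timing, mid-week contacts, full class attendance and discovery at the next contact. It also supposes that control events come out at T1 at all, which nothing in the plan ensures. The count ratios of 1.0 to 2.3 are illustrations from assumed capture rates, not estimates. The efficacy analysis is not affected. The change should be made because it improves safety capture at little cost.

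**What to change.** In section 9, add one scripted set of AE questions, identical in both arms, asked at the 3-month assessment and covering the whole period since baseline. State that any positive answer on the existing health services utilization questionnaire prompts completion of the AE form. Base any AE summary by arm on these systematically elicited events, with the number of participants questioned in each arm as the denominator, and list events volunteered in class separately. Reporting of serious events from any source stays as section 9 has it.

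The cost is a few minutes per participant at a visit already scheduled for both arms, one form and a paragraph of protocol text. The downsides are a higher recorded AE count and some recall error. That error may not be identical between arms, since participants know their allocation. Participants who miss the 3-month assessment remain uncovered.

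Brief interim messages asking the same question on the same dates in both arms would shorten the control lag, but they are optional. The reminder channel is described for class sessions, so using it for controls adds new study contact to enhanced usual care, and replies would have to be monitored.
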